Purpose:	To confirm long-term safety and reliability of BIOTRONIK's Protego DF4 lead, as used in conjunction with a BIOTRONIK DF4 compatible implantable cardioverter defibrillator (ICD) or cardiac resynchronization therapy defibrillator (CRT-D) pulse generator. The evaluation of safety will be based on the analysis of Protego lead related adverse events. The Protego DF4 registry will provide data to permit characterization of any Protego lead failures contributing to loss of bradycardia or shock therapy. Additionally, acute and chronic Protego lead parameters will be evaluated.
Subject Population:	Subjects who are indicated for an ICD or a CRT-D. Subjects must be successfully implanted with a BIOTRONIK Ilesto DF4 ICD or CRT-D or future market released BIOTRONIK DF4 ICD or CRT-D. Enrollment can be up to 30 days prior to or 30 days after implant with the DF4 system.
Enrollment:	This registry will include 1,694 subjects implanted with the Protego DF4 system. The collection of data will continue for 5 years post-implant for each enrolled subject.
Clinical Sites:	Up to 75 U.S. and International sites.
Primary Endpoints:	
 1. Evaluation of the overall incidence of adverse events (AEs) related to the Protego lead or device header 2. Evaluation of the incidence of each individual type of AE that contributes to Primary Endpoint 1
Secondary Endpoint:	
 1. Pacing threshold, sensing and impedance measurements for the Protego lead through 5 years post-implant 2. Shock impedance for the Protego lead through 5 years post-implant 3. AE rates for AEs excluded from primary safety endpoints 1 and 2, through 5 years post-implant
Clinical Events Committee Chair:	TBD
Sponsor:	BIOTRONIK, Inc. Clinical Studies Department [name]

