2.1.1 Primary Endpoint 1: Protego DF4 Lead Safety – 5-Year Adverse Event-Free Rate

The purpose of primary endpoint 1 is to evaluate the overall incidence of adverse events related to the Protego DF4 lead or header (as defined in Section 10) from implant through 5 years. Assuming that the expected Protego DF4 lead or header-related adverse event rate at 5 year post-implant (proportion of subjects with at least one AE in the timeframe from implant through 5 year post-implant) is 7.5% or less, then the primary safety endpoint will be evaluated in the following testable hypothesis in superiority format.

H₀: The adverse event-free rate (AEFR) for subjects receiving the Protego DF4 lead at 5 years post-implant is less than or equal to 92.5%

$$\text{AEFR} \leq 92.5\%$$

H_a: The adverse event-free rate (AEFR) for subjects receiving the Protego DF4 lead at 5 year post-implant is greater than 92.5%

$$\text{AEFR} > 92.5\%$$

A rejection of the null hypothesis would demonstrate that the adverse event-free rate is greater than 92.5%.

2.1.2 Primary Endpoint 2: Protego DF4 Lead Safety – Individual 5-Year Adverse Event-Free Rates

Each of the individual types of adverse events contributing to primary endpoint 1 will be evaluated separately in the following superiority hypothesis.

H₀: The individual adverse event rate (AEIndividual) for a given type of AE for the Protego DF4 lead at 5 years post-implant is greater than or equal to 1%

$$\text{AEIndividual} \geq 1\%$$

H_a: The individual adverse event rate (AEIndividual) for a given type of AE for the Protego DF4 lead at 5 years post-implant is less than 1%

$$\text{AEIndividual} < 1\%$$

If the two-sided, 95% upper confidence bound is no more than 1% for individual adverse events, then the null hypothesis will be rejected for that AE type.

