4.2 CLINICAL EVENTS COMMITTEE

A Clinical Events Committee (CEC) consisting of at least 3 independent electrophysiologists will be established to review and adjudicate adverse events that occur during the registry. The CEC will be blinded to the clinical registry site and subject identity, and to minimize bias, members will not participate as investigators. The CEC will create a registry specific charter defining the adverse event adjudication process, specifically detailing review guidelines along with appropriate response timelines.

All protocol defined adverse events included in the primary and secondary endpoint analysis (see Section 10.3.1 and Section 10.3.2) will be adjudicated by the Clinical Events Committee. The Clinical Events Committee (CEC) will have the responsibility to adjudicate the classification and category of each reported adverse event. In addition, the CEC will also indicate whether the adverse event is related, possibly related, not related, or has an unknown relation to the Protego lead.

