10.1.2 Pulse Generator-Related Adverse Events

An AE will be classified as pulse generator-related if any one of the following occurred:

- DF4 header connector malfunction
- DF4 header fluid intrusion
- Device migration
- Premature battery depletion
- Pulse generator failure
- Skin erosion

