10.2 ENDPOINT ANALYSIS

All protocol defined adverse events included in the primary and secondary endpoint analysis will be adjudicated by the Clinical Events Committee (CEC) (see Section 2.1). The CEC will have the responsibility to adjudicate the classification and category of each reported adverse event as implant procedure, implanted pulse generator, lead, or non-procedure non-system related. For each adverse event, the CEC will indicate whether the adverse event relatedness to the Protego lead is: not related, related, possibly related, or unknown.

In evaluation of the two primary endpoints for the post-approval registry, the estimates of AE rates will be based on the number of subjects with at least one "related" AE as a proportion of total subjects. Subjects with a final adjudicated related AE classification of "possibly related", "not related" or "unknown" will not have that individual event contribute to or be included in the evaluation of primary safety endpoints. The same rules will be used for purposes of Kaplan-Meier survival analyses, described in Section 2.4.2.

Secondary endpoint 3, which includes AEs that were excluded from primary safety endpoint 1 through 5 years post-implant, will also be summarized as AE rates along with their associated, exact 95% confidence intervals.

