10.3 ADVERSE EVENTS FOR THE ANALYSIS OF THE PRIMARY AND SECONDARY ENDPOINTS

10.3.1 Adverse Events for the Analysis of Primary Endpoints 1 and 2

If any of the following invasive actions occur in order to resolve an above listed Protego lead-related AE, the AE will be included in the primary safety endpoint analysis:

- Lead surgically repositioned
- Lead surgically explanted
- Lead surgically replaced
- Lead surgically abandoned
- Other lead-related surgery performed

Additionally, if any of the following non-invasive actions occur in order to resolve an above listed Protego lead-related AE, the Protego lead-related AE will be included in the primary endpoint analysis:

- Lead pacing polarity or pacing mode reprogrammed due to suspected lead failure.
- Lead abandoned and pacing disabled due to clinical failure or suspected lead failure
- Lead use continued based on medical judgment despite a known clinical failure or suspected lead failure

AEs that are corrected by reprogramming the pulse generator (other than the above) and resolved without invasive action will not be considered an adverse event counted towards the primary endpoints. For example, electrical reprogramming of the pacing polarity to eliminate extra-cardiac stimulation will not be considered an adverse event. Similarly, increasing pacing output as a result of an elevated threshold without further intervention does not count toward the primary endpoint analysis.

Subject deaths as a result of a Protego lead-related AE will be included in the primary endpoint analysis.

Primary endpoints 1 and 2 will exclude 1) lead dislodgements that occur within 30 days after lead implant or a lead revision procedure and 2) high pacing threshold, intermittent capture, no lead capture within 30 days after lead implant or a lead revision procedure. However, these will count towards the adverse event secondary endpoint.

In addition, the following two pulse generator-related adverse events will be included in the analysis of primary endpoints 1 and 2: DF4 header connector malfunction and DF4 header fluid intrusion.

10.3.2 Adverse Events for the Analysis of Secondary Endpoint 3

If any of the following invasive actions occur in order to resolve an above listed RA or LV lead-related AE, the AE will be included in the secondary endpoint analysis:

- Lead surgically repositioned
- Lead surgically explanted
- Lead surgically replaced
- Lead surgically abandoned
- Other lead-related surgery performed

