APPENDIX A: DEFINITION OF TERMS

AE (Adverse Event) – An unwanted affect detected in participants either implant procedure-related, pulse generator-related, lead-related, or other. The term is used whether or not the effect can be attributed to the leads in the study. For the purposes of this study, the CEC will indicate whether the adverse event relatedness to the Protego lead is: not related, related, possibly related, or unknown.

ACC/AHA – American College of Cardiology/American Heart Association

Cardiac Perforation – Penetration of the lead tip through the myocardium (including microperforation), either clinically suspected or confirmed by chest x-ray, fluoroscopy, echocardiogram, intracardiac electrogram and/or visually.

CEC – Clinical Events Committee

Clinical Failure – Inability of the lead to correctly sense or pace in the heart, not attributable to a mechanical malfunction of the lead or pulse generator that remains unresolved despite reprogramming and/or repositioning.

CFR – Code of Federal Regulations

Conductor Fracture – See Lead Fracture

Confirmed Failure – A lead having clinically relevant characteristics that are outside the performance limits established by BIOTRONIK while implanted and in service, as confirmed by analysis, except for changes in characteristics that are due to induced malfunctions. Lead damage caused during or after explant is not considered a failure.

Chronic Threshold – Chronic threshold is defined as the pacing threshold determined at the subject's 3 month follow-up visit.

eCRF – Electronic Case Report Form

EDC – Electronic Data Capture system

Exit Block – The failure of an intact pacing system to capture the heart because the stimulation threshold exceeds the output of the pacemaker.

Explantation – Surgical removal of a lead during the acute implant stage, whereby the lead has not been chronically implanted and can be easily removed by simple traction.

Extracardiac Stimulation – Clinical observation of inadvertent nerve/muscle stimulation other than cardiac muscle, such as the diaphragm or pectoral muscles.

Extraction of a Lead – Surgical removal of a chronically implanted lead.

Failure to Capture or Loss of Capture – Intermittent or complete failure to achieve cardiac stimulation at programmed output delivered outside of the cardiac refractory period.

High Pacing Threshold – One of the following definitions must be met:

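### Sections 10.2 and 10.3.1 conflict on whether DF4 header events count toward primary endpoints 1 and 2, and the plan does not say which governs

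*Combined protocol and SAP*

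**What the plan says.** The endpoint definitions cover the header. The Summary gives the first primary endpoint as "Evaluation of the overall incidence of adverse events (AEs) related to the Protego lead or device header", and Section 2.1.1 sets out to evaluate the "overall incidence of adverse events related to the Protego DF4 lead or header". Section 10.3.1 carries this through: after listing the lead events that qualify, it adds that "the following two pulse generator-related adverse events will be included in the analysis of primary endpoints 1 and 2", and names header connector malfunction and header fluid intrusion. It attaches no relatedness condition to them. Section 10.1.2 lists both under the rule "An AE will be classified as pulse generator-related if any one of the following occurred", so neither is classed as a lead event.

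The counting rule looks only at the lead. Section 4.2 has the CEC rate each event as "related, possibly related, not related, or has an unknown relation to the Protego lead". Appendix A repeats this: "the CEC will indicate whether the adverse event relatedness to the Protego lead is: not related, related, possibly related, or unknown". Section 10.2 uses the same scale and builds both primary endpoints from subjects with at least one event rated *related*. Subjects whose event is rated *possibly related*, *not related* or *unknown* "will not have that individual event contribute to or be included in the evaluation of primary safety endpoints". It then adds: "The same rules will be used for purposes of Kaplan-Meier survival analyses". It makes no exception for header events.

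**The concern.** A header fault with a sound lead is in the primary endpoints under 10.3.1 and out under 10.2. So is any header event that the CEC rates *possibly related* or *unknown* with respect to the lead. The two sections can also be read as successive filters, with 10.3.1 naming the eligible event types and 10.2 then screening each event. On that reading most pure header events are lost.

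The choice changes the count for two event types in endpoint 2 and for the total in endpoint 1. An analyst could make it after the header events are known. The literal 10.2 reading biases the adverse event-free rate upward. It also keeps these events out of the Kaplan-Meier curves that Section 2.4.2 compares with the 92.5% and 99% targets, where a shortfall triggers a report to FDA.

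These events are close to what is new in the product. Section 1.4.2 limits the design change from the predecessor lead to the connector and the adjoining transition area, and Section 1.4.3 says that DF4 needs a more complex generator connector cavity with strict sealing requirements.

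**Working it through.** **One event under both rules.** Take fluid intrusion into the header, with the lead sound and rated *not related*.

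| Section | Rule applied | Counts in endpoints 1 and 2? |
|---|---|---|
| Summary, 1.2, 2.1.1 | Lead or header events | Yes |
| 10.1.2 | Pulse generator class | No rule given |
| 10.3.1 | Named as included, no relatedness condition | Yes |
| 10.2 | Not rated *related* to the lead | No, and not in the Kaplan-Meier curves |

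A header event rated *related* to the lead counts under both sections, so the conflict is confined to header events with any other rating.

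**Inputs** (Sections 2.3 and 2.4.1): exact binomial test, one-sided alpha 0.025, performance goal 92.5% (event rate 7.5%), expected event-free rate 95.0%, 750 evaluable subjects for endpoint 1 and 1000 for endpoint 2. Endpoint 2 passes for an event type if the exact two-sided 95% upper bound is below 1%.

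**The plan's own figures.** At n = 750 the test rejects with at most 42 subjects with an event: P(X ≤ 42 | 750, 7.5%) = 2.47%, and the power at a 5% event rate is 80.1%. This agrees with the stated 750 and 80%. Attrition gives 750/0.9⁵ = 1270.1, rounded up to 1271, and 1000/0.9⁵ = 1693.5, rounded up to 1694. The sample sizes do not depend on the conflict.

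**Endpoint 1.** Let h be the 5-year proportion of subjects whose only primary event is a header event left uncounted under 10.2. The documents give no value for h, so a range is assumed. With the true lead-or-header rate at the null, the counted rate is 7.5% − h, and the false-pass risk is P(X ≤ c | n, 7.5% − h), where c = 42 for n = 750 and c = 58 for n = 1000.

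| h | Counted rate | n = 750 | n = 1000 |
|---|---|---|---|
| 0 | 7.5% | 2.47% | 2.08% |
| 0.1% | 7.4% | 3.11% | 2.74% |
| 0.5% | 7.0% | 7.28% | 7.41% |
| 1.0% | 6.5% | 17.80% | 20.38% |

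If the header-only rate is 1% but only half of those events go uncounted, the counted rate is 7.5% − 0.5% = 7.0%, which is the third row: 7.3% or 7.4%.

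**Endpoint 2, n = 1000.** The exact upper bounds are 0.368% for 0 events, 0.874% for 3 and 1.021% for 4, so an event type passes with at most 3 counted events. For a header event type with a true rate of 1%, of which a share s is counted, P(pass) = P(X ≤ 3 | 1000, s × 1%):

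| Share counted | Counted rate | P(pass) |
|---|---|---|
| All | 1.0% | 1.0% |
| Half | 0.5% | 26.4% |
| None | 0 | 100% |

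**The case against.** The strongest reply is that the intent is not in doubt. The Summary, 1.2, 2.1.1 and 10.3.1 all place header events in the primary endpoint, the inclusion in 10.3.1 is specific, and the literal 10.2 reading leaves that sentence with almost nothing to do. A specific provision would normally prevail over a general one. This is a fair account of what was probably meant. It does not supply the missing rule: 10.2 is also specific, since it defines the numerator of both primary endpoints without exception.

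Other points have some weight:

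- **CEC charter.** It may say how header events are rated, and the CEC could rate some faults at the lead-header interface as *related* to the lead. Neither possibility changes the wording of 10.2.
- **Backstops.** Header events stay reportable, and 2.4.2 requires root causes to be investigated. Under 10.3.2 those needing invasive intervention reach secondary endpoint 3; on the broader definition of that endpoint in 2.1.3, perhaps all adjudicated ones do. They would not go undetected. But 2.1.3 attaches no hypothesis test to that endpoint.
- **Size.** The null boundary, full non-counting and a 1% header-only rate together make a severe case. If the true total rate is the expected 5% and h is 0.1%, the pass probability at n = 1000 moves only from 88.9% to 91.5%, and a pass is then the right answer. At h = 0.1% even the null-boundary risk moves only from 2.1% to 2.7%.
- **Remedy.** A separate rating of relatedness to the header would also resolve the conflict, but it adds an adjudication step.

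**Conclusion.** The concern holds, and the plan should be corrected. 10.2 as written can remove from both primary endpoints, and from the Kaplan-Meier monitoring, header events that the endpoint definition and 10.3.1 include. No text settles which section governs. The conflict covers only header events not rated *related* to the lead.

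For endpoint 1 the effect is small if such events are rare and material if they approach 0.5% to 1% of subjects. For endpoint 2 the choice of reading can by itself decide the result for a header event type. These sizes rest on an assumed header rate, an assumed share uncounted and, for endpoint 1, a true total rate at the 7.5% null. The textual conflict rests on none of these.

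**What to change.** Add one sentence to 10.2: events that the CEC adjudicates as DF4 header connector malfunction or as DF4 header fluid intrusion count toward primary endpoints 1 and 2 and the Kaplan-Meier analyses, regardless of the rating of relatedness to the Protego lead. Align the wording of 4.2 and Appendix A with it; this is for consistency, since the sentence in 10.2 resolves the conflict. Make the change before header events are adjudicated.

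The CEC already adjudicates classification and category, so no new rating, subjects, visits or adjudicators are needed. The one downside is that the reported adverse event-free rate may be slightly less favourable.

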2.4.2 Trend Analyses

The primary safety endpoints are evaluated at 5 years post-implant against pre-specified performance levels (92.5% for overall freedom from Protego lead-rated AEs, 1% for individual AE rates). To monitor the ongoing incidence of any potential AEs against the accumulating follow-up exposure post-implant, Kaplan-Meier survival curves will be prepared at the reporting intervals for these safety outcomes. Root causes for any failures, regardless of the incidence rates, will be investigated.

If the observed cumulative survival rates fall below the 5-year target values (92.5% of overall freedom from AEs, 99% for individual AEs) at any time during the registry, or are projected to fall below the target values, then BIOTRONIK will summarize the observed data and the results of its failure investigations, and report the findings to the FDA at or before the next scheduled status report. If at any time a single unanticipated adverse event or device failure, or combination of events, is believed to have implications regarding the safety of current or future subjects, then this will be reported to the FDA within the statutory timeframes.

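### Section 10.2 can remove DF4 header events that Sections 2.1.1 and 10.3.1 place in the primary endpoints; a descriptive curve that counts uncertain adjudications would also be a cheap addition

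*Combined protocol and SAP*

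**What the plan says.** **Scope of the endpoints.** Section 2.1.1 sets out to "evaluate the overall incidence of adverse events related to the Protego DF4 lead or header" through 5 years. Section 10.3.1 adds that "the following two pulse generator-related adverse events will be included in the analysis of primary endpoints 1 and 2", naming DF4 header connector malfunction and DF4 header fluid intrusion. Section 10.1.2 lists both as pulse generator-related.

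**Adjudication.** Under Section 4.2 the CEC marks each event as "related, possibly related, not related, or has an unknown relation to the Protego lead". Section 10.2 and the adverse event entry in Appendix A use the same four categories, again with respect to the lead. None of them has a scale for the header.

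**Counting rule.** Section 10.2 counts subjects with at least one *related* event. An event with any other label "will not have that individual event contribute to or be included in the evaluation of primary safety endpoints". It continues: "The same rules will be used for purposes of Kaplan-Meier survival analyses, described in Section 2.4.2".

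**Uncertain lead events.** Section 10.3.1 admits lead events on the strength of the action taken, for example "Lead abandoned and pacing disabled due to clinical failure or suspected lead failure". Appendix A defines a suspected lead failure as only potentially a malfunction.

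**Monitoring.** Section 2.4.2 requires a report to FDA "If the observed cumulative survival rates fall below the 5-year target values" (92.5% overall, 99% for individual types) at any time, or if they are projected to. It also says: "Root causes for any failures, regardless of the incidence rates, will be investigated".

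**The concern.** There are two separate issues.

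1. **Header events.** A fault confined to the generator's connector cavity is naturally scored *not related* to the lead. Section 10.3.1 then says it counts, and Section 10.2 says it does not. The DF4 connection is the main change from the predecessor lead (Sections 1.3 and 1.4.2), and Section 1.4.3 describes the DF4 connector cavity as more complex. These are therefore events the registry exists to detect. Two analysts could reach opposite endpoint 2 results from the same data.

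2. **Uncertain lead events.** Section 10.3.1 admits events acted on for a suspected failure, so some *possibly related* or *unknown* labels are foreseeable. Section 10.2 takes these out of both primary endpoints and the monitoring curves. No planned rate or curve combines them with the *related* events, so a reader cannot see how sensitive the result is to the label.

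**Working it through.** **Plan's own figures.** For endpoint 1, an exact binomial test at n = 750 against 92.5% passes with at most 42 subjects with events (one-sided alpha 0.0247, power 0.801 at 95.0%). Attrition gives 750/0.9^5 = 1270.1, so 1271, and 1000/0.9^5 = 1693.5, so 1694. All reproduce.

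**Part 1: header events and endpoint 2.** The exact two-sided 95% upper limit for x events in n is the 0.975 quantile of Beta(x + 1, n − x). Section 2.4.1 requires it to be below 1%. With n = 1000 (Section 2.3):

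| Counted events of one type | Upper limit | Result |
|---|---|---|
| 0 | 0.368% | pass |
| 3 | 0.874% | pass |
| 4 | 1.021% | fail |

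Four connector malfunctions fail if Section 10.3.1 governs. If Section 10.2 removes one, the type passes; if it removes all four, the limit is 0.368%. The boundary shifts with the evaluable number. At n = 1024, four events give about 1.021% × 1000/1024 = 0.997%, so the deciding event becomes the fifth (1.163% × 1000/1024 = 1.136%). A single event still decides.

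**Part 2: where filtered lead events go.** Sections 2.1.3, 2.4.1 and 10.2 send events excluded from the primary endpoints to secondary endpoint 3, with exact 95% intervals and no hypothesis test. Section 10.3.2 shows that this endpoint also holds procedure, generator and RA/LV lead events. Its carry-over sentence cites only the exclusions listed in Section 10.3.1. Filtered events are therefore covered in general terms, but not as a lead rate.

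**Part 2: possible size.** Let f be the share of truly lead-caused events not labelled *related*. The documents do not give f. The figures below assume that every uncounted event is lead-caused, with N = 1694, constant hazards and 10% independent yearly attrition.

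- *Endpoint 1 test at a true rate of 7.5%.* Section 2.4.3 keeps only subjects who reach 5 years or have had an event. At f = 0 the expected observed rate is therefore 9.67%, on a mean of 1024 subjects. The false-pass probability is under 0.1% at f = 10% and 0.7–1.1% at f = 20%. It reaches the nominal 2.5% at f of about 23–25% (12–13% with 5% yearly attrition).
- *Overall Kaplan-Meier curve.* The expected curve meets 92.5% at a true rate of 1 − 0.925^(1/(1 − f)), or 7.5%/(1 − f) if uncounted subjects stay as non-events. This gives 8.3% at f = 10%, 9.3–9.4% at 20% and 11.0–11.3% at one third. At a true 9%, the 5-year estimate falls below 92.5% with probability 97% at f = 0, 78–80% at 10%, 34–38% at 20% and 1–2% at one third.
- *Individual 99% limb.* Take the primary-event mix in Table 1 (13, 5, 5, 5, 2 and 1 of 31) as an illustration. At a true 9% and f = one third, about 9% × 2/3 = 6.0% is counted, and oversensing alone accounts for 6.0% × 13/31 = 2.5%, well past 1%. In simulation this limb fires in 99.5–100% of runs. If events were instead spread evenly over 17 types (15 in Section 10.1.3 plus the two header events), each would be 6.0%/17 = 0.35%, and either limb would fire in only about 5% of runs.

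**The case against.** **On header events.** Section 10.3.1 is specific and mandatory, and Section 2.1.1 supports it. Reading the specific clause over the general filter is natural, and Section 2.3 calls the endpoint 2 comparison non-powered. All of this stands. It makes the conflict easy to cure but does not remove it: no section exempts the two events from Section 10.2, and the CEC is given no header question. The CEC charter might address it, but it is not among the documents.

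**On uncertain lead events.** The related-only rule is pre-specified and matches the endpoint wording. Filtered events reach secondary endpoint 3, root causes are investigated whatever the rate, and Section 10.1.3 records confirmed, suspected or no lead integrity failure for each lead event. This also stands, so the missing curve is a gap in sensitivity analysis and not an error.

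Two stronger readings are tempting, and the documents do not support either.

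- *The filter inflates the endpoint 1 error rate.* A binomial calculation with n fixed at 750 suggests this: the chance of passing at a true 7.5% rises from 2.5% to 11.7% at f = 10% and 35.8% at 20%. It ignores the Section 2.4.3 evaluable rule, which pushes the observed rate up and more than offsets modest values of f under the planned attrition.
- *The filter silences FDA reporting.* The 97% to 1–2% series covers only the overall limb at 5 years. Reporting also follows from any single type falling below 99%, from earlier looks and from projections. With the Table 1 mix, the 99% limb alone fires almost always at a true 9%.

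**Conclusion.** The header conflict is an error in the text and affects the primary endpoints. Section 10.2 *can* remove header events. Whether it would depends on how the CEC codes them, so it should not be inferred that they are certain to be lost. One event can reverse endpoint 2 for a header event type. That conclusion does not depend on f.

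The absence of a related-plus-uncertain lead curve is a smaller matter and a worthwhile improvement. Its effect cannot be sized from the documents. On the stated assumptions, modest shares of uncertain labels do not inflate the endpoint 1 test. They do lower the overall curve's chance of crossing 92.5%, but those figures are not probabilities of FDA reporting, which depend heavily on how events spread over types. The Table 1 mix comes from the predecessor lead's registry and is only illustrative.

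**What to change.** 1. **Required.** Amend Sections 4.2 and 10.2 so that the CEC also records relatedness to the DF4 header. State that the two header events count in primary endpoints 1 and 2, and in the Section 2.4.2 curves, when adjudicated related to the header or the lead. Cost: a sentence or two of text and one added adjudication item.

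2. **Recommended.** Keep related-only as the primary rule. In Sections 10.2 and 2.4.2, pre-specify a descriptive Kaplan-Meier sensitivity analysis, overall and by event type, that also counts *possibly related* and *unknown* Protego lead or header events meeting Section 10.3.1. Events scored *not related* to both lead and header stay out. Show it with confidence bounds beside the related-only curve at each reporting interval and at 5 years, not as a success hurdle. Cost: one more set of curves, built from labels the CEC will already hold.

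The downside of the second change is a less favourable rate that may include events the lead did not cause. The documents also do not show that 92.5% was set for an inclusive definition, and the report should say so. The curve would remain readable. With 10% yearly attrition the 5-year standard error is 0.61 points at a 5% rate and 0.66 at 6%, so the expected 95% intervals are 95.0 ± 1.96 × 0.61 = 93.8–96.2% and 94.0 ± 1.96 × 0.66 = 92.7–95.3%. Neither change requires altering the Section 2.4.3 denominator.
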